## 10.10. Appendix 10: Criteria for Assessing Potential Cases of Anaphylaxis

**Anaphylaxis is highly likely when any one of the following 3 criteria are fulfilled (Sampson 2006):**

1. Acute onset of an illness (minutes to several hours) with involvement of the skin, mucosal tissue, or both (eg, generalized hives, pruritus or flushing, swollen lips-tongue-uvula)

AND AT LEAST ONE OF THE FOLLOWING:

- a. Respiratory compromise (eg, dyspnea, wheeze-bronchospasm, stridor, reduced PEF, hypoxemia)
  - b. Reduced BP or associated symptoms of end-organ dysfunction (eg, hypotonia [collapse], syncope, incontinence)
2. Two or more of the following that occur rapidly after exposure to a likely allergen for that participant (minutes to several hours):
    - a. Involvement of the skin-mucosal tissue (eg, generalized hives, itch-flush, swollen lips-tongue uvula)
    - b. Respiratory compromise (eg, dyspnea, wheeze-bronchospasm, stridor, reduced PEF, hypoxemia)
    - c. Reduced BP or associated symptoms (eg, hypotonia [collapse], syncope, incontinence)
    - d. Persistent gastrointestinal symptoms (eg, crampy abdominal pain, vomiting)
  3. Reduced BP after exposure to known allergen for that participant (minutes to several hours):
    - a. Infants and children: low systolic BP (age specific) or greater than 30% decrease in systolic BP\*
    - b. Adults: systolic BP of less than 90 mm Hg or greater than 30% decrease from that person's baseline

Key: BP=blood pressure; PEF=Peak expiratory flow

\*Low systolic blood pressure for children is defined as less than 70 mm Hg from 1 month to 1 year, less than (70 mm Hg + [2 x age]) from 1 to 10 years, and less than 90 mm Hg from 11 to 17 years.

### 10.11. Appendix 11: Hepatitis B Virus (HBV) Screening with HBV DNA

Participants must undergo screening for hepatitis B virus (HBV). At a minimum, this includes testing for HBsAg (HBV surface antigen), anti-HBs (HBV surface antibody), and anti-HBc total (HBV core antibody total):

- Participants who test negative for all HBV screening tests (ie, HBsAg-, anti-HBc-, and anti-HBs-) **are eligible** for this protocol.
- Participants who test **negative** for surface antigen (HBsAg-) and test **positive** for core antibody (anti-HBc+) **and** surface antibody (anti-HBs+) **are eligible** for this protocol.
- Participants who test **positive only** for **surface antibody** (anti-HBs+) **are eligible** for this protocol.
- Participants who test **positive** for surface antigen (HBsAg+) **are NOT eligible** for this protocol, regardless of the results of other hepatitis B tests.
- Participants who test **positive only** for **core antibody** (anti-HBc+) must undergo further testing for the presence of hepatitis B virus deoxyribonucleic acid (HBV DNA) test. If the HBV DNA test is **negative**, the participant **is eligible** for this protocol. If the HBV DNA test is **positive**, the participant **is NOT eligible** for this protocol. In the event the HBV DNA test cannot be performed, the participant **is NOT eligible** for this protocol.

These eligibility criteria based on HBV test results are also represented in table below. For participants who are eligible with surface antigen (HBsAg) negative, core antibody (anti-HBc) and/or surface antibody (anti-HBs) positive, and HBV DNA test is negative, HBV DNA quantitation should be monitored according to local guidelines.

Eligibility based on hepatitis B virus test results			
HEPATITIS B TEST RESULT			STATUS
Hepatitis B surface antigen (HBsAg)	Hepatitis B surface antibody (anti-HBs)	Hepatitis B core antibody (anti-HBc total)	
negative	negative	negative	Eligible
negative	(+)	negative	
negative	(+)	(+)	
(+)	negative or (+)	negative or (+)	Not eligible
negative	negative	(+)	(Require testing for presence of HBV DNA*)

\* If HBV DNA is detectable, the participant is not eligible for this protocol. If HBV DNA testing cannot be performed, or there is evidence of chronic liver disease, the participant is not eligible for the protocol.

For participants who **are not eligible for this protocol due to HBV test results**, consultation with a physician with expertise in the treatment of HBV infection is recommended.

**10.12. Appendix 12: Protocol Amendment History**

This is an original protocol.

## VERSION HISTORY

**Table [xx] – SAP Version History Summary**

| SAP Version | Approval Date | Change  | Rationale |
|--------------------|----------------------|----------------|------------------|
| 1                  |                      | Not Applicable | Initial release  |
|                    |                      |                |                  |
|                    |                      |                |                  |
|                    |                      |                |                  |
|                    |                      |                |                  |

## 1. INTRODUCTION

77242113PSO2003 is a randomized, double-blind placebo-controlled, parallel, multicenter, interventional study in participants with moderate-to-severe plaque psoriasis. This Phase 2a study is focused on proof of-concept and will assess the efficacy, safety, and tolerability of JNJ-77242113 (an IL-23R peptide antagonist) orally administered as a delayed release tablet formulated with CCI [REDACTED]. This study will be conducted in parallel with the complementary study 77242113PSO2001, a Phase 2b randomized, double-blinded, dose-ranging, placebo-controlled study designed to evaluate the efficacy and safety of JNJ-77242113, formulated as an immediate-release oral tablet CCI [REDACTED] in adults with moderate-to-severe plaque psoriasis. The target population for this study intervention consists of participants 18 to 75 years of age (or the legal age of consent if it is higher in the jurisdiction in which the study is taking place), with moderate to severe psoriasis of at least 26 weeks duration, primarily defined as a total BSA  $\geq 10\%$ , total PASI  $\geq 12$ , and total Investigator Global Assessment (IGA)  $\geq 3$  at screening and baseline.

This Statistical Analysis Plan (SAP) contains definitions of analyses sets, derived variables and address the statistical methods for all planned analyses for the study.

### 1.1. Objectives and Endpoints

| Objectives  | Endpoints   |
|---|---|
| Primary  |   |
| To evaluate the efficacy of an oral tablet formulation of JNJ-77242113 compared with placebo in participants with moderate-to-severe plaque psoriasis.                    | 
 
Proportion of participants achieving PASI 75 (<math>\geq 75\%</math> improvement from baseline in PASI) at Week 16
 
  |
| Secondary  |   |
| To assess the safety and tolerability of an oral tablet formulation of JNJ-77242113 compared with placebo in participants with moderate-to-severe plaque psoriasis.       | 
 
Frequency and type of adverse events (AEs) and serious adverse events (SAEs).
 
   |
| To evaluate additional measures of efficacy of an oral tablet formulation of JNJ-77242113 compared with placebo in participants with moderate-to-severe plaque psoriasis. | 
 
Change from baseline in PASI total score at Week 16.
 
Proportion of participants achieving PASI 90 (<math>\geq 90\%</math> improvement from baseline in PASI) at Week 16.
 
Proportion of participants achieving PASI100 (100% improvement from baseline in PASI) at Week 16.
 
Proportion of participants achieving an Investigator Global Assessment (IGA) score of cleared (0) or minimal (1) at Week 16.
 
Proportion of participants achieving an IGA score of cleared (0) at Week 16.
 
Change from baseline in body surface area (BSA) at Week 16.
 
 |
| Exploratory  |   |

| Objectives  | Endpoints  |
|---|--|
| To characterize the pharmacokinetics (PK) of JNJ-77242113 for the oral tablet formulation and explore the PK/pharmacodynamic (PD) relationship of the JNJ-77242113 formulation for biomarkers, efficacy, and safety in participants with moderate-to-severe plaque psoriasis. | 
 
• JNJ-77242113 PK parameters (ie, plasma concentration just prior to the beginning or at the end of a dosing interval Ctrough], area under the plasma concentration versus time curve [AUC]).
 
• The relationship between PK parameters and PD (ie, skin, blood cellular and molecular biomarker activity as well as clinical endpoints and safety parameters).
 
   |
| To explore treatment effects of an oral tablet formulation of JNJ-77242113 on biomarkers in participants with moderate-to-severe plaque psoriasis.  | 
 
• Change from baseline in levels of skin and blood biomarkers.
 
   |
| To evaluate the immunogenicity of JNJ-77242113.   | 
 
• The incidence of anti-drug antibodies to JNJ-77242113.
 
   |
| To further assess the safety and tolerability of an oral tablet formulation of JNJ-77242113 compared with placebo in participants with moderate-to-severe plaque psoriasis.   | 
 
• Frequency and type of AEs, SAEs, reasonably related AEs, and AEs leading to discontinuation of study intervention.
 
• Laboratory parameters and change from baseline in laboratory parameters (hematology and chemistry) over time.
 
• Systolic and diastolic blood pressures over time.
 
   |
| To evaluate the treatment effect of an oral tablet formulation of JNJ-77242113 on patient-reported psoriasis severity and dermatology-specific health-related quality of life compared with placebo in participants with moderate-to-severe plaque psoriasis.                 | 
 
• Change from baseline in Psoriasis Symptoms and Signs Diary (PSSD) symptoms score at Week 16.
 
• Change from baseline in PSSD signs score at Week 16.
 
• Proportion of participants achieving a PSSD symptoms score=0 at Week 16 among participants with a baseline symptom score <math>\geq 1</math>.
 
• Proportion of participants achieving a PSSD signs score=0 at Week 16 among participants with baseline sign scores <math>\geq 1</math>.
 
• Proportion of participants achieving a Dermatological Life Quality Index (DLQI) score of 0 or 1 at Week 16 among participants with baseline DLQI score <math>> 1</math>.
 
 |

## 1.2. Study Design

This is a randomized, double-blind placebo-controlled, parallel, multicenter, interventional study in participants with moderate-to-severe plaque psoriasis. This Phase 2a study is focused on proof of-concept and will assess the efficacy, safety, and tolerability of JNJ-77242113 (an IL-23R peptide antagonist) orally administered as a delayed release tablet formulated with an CCI [REDACTED]

[REDACTED] This study will be conducted in parallel with the complementary study 77242113PSO2001, a Phase 2b randomized, double-blinded, dose-ranging, placebo-controlled study designed to evaluate the efficacy and safety of JNJ-77242113, formulated as an immediate-release oral tablet CCI [REDACTED] in adults with moderate-to-severe plaque psoriasis. The target population for this study intervention consists of participants 18 to 75 years of age (or the legal age of consent if it is higher in the jurisdiction in which the study is taking place), with moderate to severe psoriasis of at least 26 weeks duration, primarily defined as a total BSA  $\geq 10\%$ , total PASI  $\geq 12$ , and total Investigator Global Assessment (IGA)  $\geq 3$  at screening and baseline.

A target of 80 participants will be enrolled in this study. Participants will be randomized to receive 1 of the 2 JNJ-77242113 doses of an oral delayed release tablet CCI [REDACTED] or placebo in a 3:3:2 ratio (30:30:20) using dynamic central randomization, stratified by baseline weight ( $\leq 90$  kg,  $>90$  kg).

The treatment arms for this study will be as follows:

**Group 1:** 10 mg JNJ-77242113 oral delayed release tablet CCI [REDACTED] administered once daily from Week 0 through Week 16.

**Group 2:** 50 mg JNJ-77242113 oral delayed release tablet CCI [REDACTED] administered once daily from Week 0 through Week 16.

**Group 3:** Placebo oral delayed release tablet, administered once daily from Week 0 through Week 16.

[figure not shown]
Participants will be instructed to take the study intervention once daily on an empty stomach, at least 2 hours after final food and caloric drink consumption in the evening (water is permitted). The study intervention should be administered with approximately 240 mL (8 ounces) of noncarbonated water. The tablet must be swallowed whole (ie, intact), and participants must not chew, divide, dissolve, or crush the study intervention. Participants should not consume food or drinks, except for water, after study intervention administration until the following morning. Following a 16-week placebo-controlled treatment period, participants will return for a follow-up visit approximately 4 weeks after the last administration of study intervention.

There is 1 database lock (DBL) planned at the end of this intervention cohort. An interim analysis (IA) is planned at Week 8 to inform Phase 3 development. Additional ad hoc IA(s) may be conducted if deemed necessary. No DBLs are planned for any of the IA(s). An external

Independent Data Monitoring Committee (iDMC) will be commissioned to assess the safety at an ongoing basis for this study.

A study design schematic is provided in Figure 1 below.

**Figure 1: Schematic Overview of the Study**

Abbreviations: IA = interim analysis; PE = primary endpoint; QD = quaque die (once a day)

## 2. STATISTICAL HYPOTHESES

The hypothesis of this study is that an oral delayed release tablet formulation of JNJ-77242113 CCI will result in superior efficacy compared with placebo as determined by the proportion of participants achieving PASI 75 response at Week 16.

## 3. SAMPLE SIZE DETERMINATION

This study is designed to assess the clinical response, safety/tolerability, and pharmacology of JNJ-77242113 CCI in participants with moderate-to-severe plaque psoriasis. The sample size is evaluated based on the primary endpoint of a PASI 75 response at Week 16. The sample size of 80 participants was chosen in order to have sufficient power to detect a difference between the JNJ-77242113 CCI (30 participants for each of low and high dose groups) and the placebo group (20 participants).

The assumptions for the sample size and power calculations were mainly based on the clinical data from guselkumab Phase 3 clinical studies that evaluated the safety and efficacy in the treatment of adult participants with moderate-to-severe plaque psoriasis.

The null hypothesis is to be tested at an overall Type 1 error rate of 0.10 (2-sided). Assuming PASI75 response rates at Week 16 are 5% to 10% for placebo and 40% to 80% for JNJ-77242113 CCI, a sample size of 20 participants in the placebo group and 30 participants in the JNJ-77242113 CCI will provide at least 90% power to detect a 35% difference between the JNJ-77242113 CCI and placebo groups in the proportion of participants achieving a PASI 75 response at Week 16 based on a 2-sample Z-test.

## 4. POPULATIONS (ANALYSIS SETS) FOR ANALYSIS

Unless specified otherwise, data included in the analyses for the study are briefly summarized below:

**Table 1: Populations for Analyses**

| Population                  | Description   |
|-----------------------------|---|
| Enrolled                    | All participants who signed the ICF   |
| Randomized                  | All participants who were randomized in the study   |
| FAS                         | All randomized participants who took at least 1 dose of study intervention  |
| Per Protocol (PP)           | The per protocol analysis set (PP) includes a subset of participants in the full analysis set (FAS) who were in compliance with the protocol. Compliance is defined as participants in FAS and meet the following criteria: 
 
Has a total BSA <math>\geq 10\%</math> at the screening and baseline visit.
 
Has a total PASI score <math>\geq 12</math> at the screening and baseline visit
 
Has a total IGA score <math>\geq 3</math> at the screening and baseline visit
 
Overall compliance of study treatment at least 80% prior to Week 16, Or participants who did not complete all scheduled study intervention administration due to intercurrent events (i.e., discontinued the study intervention due to lack of efficacy, an AE of worsening of psoriasis, or started a protocol-prohibited medication or therapy during the study that could improve psoriasis)
 
Criteria added as needed after the team's review.
 
 |
| Safety Analysis Set         | All randomized participants who took at least 1 dose of study intervention  |
| PK Analysis Set             | All randomized participants who received at least 1 dose of JNJ-77242113 CCI and had at least 1 valid blood sample drawn for PK analysis after their first dose of JNJ-77242113 CCI   |
| Immunogenicity Analysis Set | All randomized participants who received at least 1 dose of JNJ-77242113 CCI and who had at least 1 sample obtained after the first dose of JNJ-77242113 for the detection of antibodies to JNJ-77242113  |
| PD Analysis Set             | All randomized participants who received at least 1 dose of JNJ-77242113  |

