#### **6.4. Study Intervention Compliance**

Participant compliance with study intervention will be assessed at each visit during the treatment period by counting returned tablets.

A participant will be considered noncompliant if they miss more than 20% of the prescribed doses of study intervention during the study, unless study intervention is withheld for safety reasons. Similarly, a participant will be considered significantly noncompliant if they are judged by the investigator to have intentionally or repeatedly taken 20% or more than prescribed amount of study intervention during the study.

If a participant's study intervention intake is not according to the protocol, the investigator will take the necessary measures to ensure future adherence to the protocol. If necessary, the participant may be discontinued from study intervention by the investigator or medical monitor (Section 7, Discontinuation of Study Intervention and Participation Discontinuation/Withdrawal).

Study intervention compliance will be further detailed in the statistical analysis plan (SAP).

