#### 5.3.3.4. Per Protocol Analysis

The primary efficacy endpoint will be evaluated in the PP population based on the primary estimand except that ICE 3 will not be applied. Participants with ICE 3 who do not complete all scheduled study administration prior to Week 16 will be excluded from the per protocol analysis. The same data handling rule and analysis method specified in Section 5.3.3.1 will be applied.

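### The SAP's per-protocol rule drops the 80% compliance test, even for doses before the stop, when dosing ended because of intercurrent event 1 or 2, and it has no upper limit, so some participants whom the protocol calls noncompliant enter the set

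*SAP*

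**What the plan says.** SAP Section 4, Table 1 (Populations for Analyses) builds the PP set from FAS participants who meet the BSA, PASI and IGA entry thresholds and one dosing criterion. That criterion has two branches, the second starting at the word Or: "Overall compliance of study treatment at least 80% prior to Week 16, Or participants who did not complete all scheduled study intervention administration due to". The table limits the causes in the second branch to ICE 1 (stopping for lack of efficacy or an adverse event of worsening psoriasis) and ICE 2 (starting a prohibited therapy that could improve psoriasis). The last bullet reads "Criteria added as needed after the team's review".

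Protocol 6.4 defines noncompliance in both directions. A participant is "noncompliant if they miss more than 20% of the prescribed doses of study intervention during the study, unless study intervention is withheld for safety reasons". A participant is significantly noncompliant if the investigator judges that they have "intentionally or repeatedly taken 20% or more than prescribed amount of study intervention during the study". The same section leaves further compliance detail to the SAP.

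SAP 5.3.3.4 analyses the PP set under the primary estimand without ICE 3 (stopping for any other reason). It adds one exclusion: "Participants with ICE 3 who do not complete all scheduled study administration prior to Week 16 will be excluded from the per protocol analysis". It otherwise applies the data handling of SAP 5.3.3.1, where ICE 1 or 2 before Week 16 makes the participant a PASI 75 non-responder. SAP 6.7 (Appendix 7) defines compliance as doses taken over doses due and tabulates a category above 100%, but does not link that category to the PP set.

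**The concern.** The second branch has a sound purpose: doses not taken after a treatment failure should not count against the participant. As worded, it also removes any requirement on adherence before the stop. The first branch sets only a lower limit, so over-taking never disqualifies anyone, although the protocol treats it as the more serious form of noncompliance.

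Adherence is therefore judged inconsistently. A completer just under 80% is out, while a much less adherent participant who stopped early for ICE 1 or 2 is in and counts as a failure. The protocol (9.4.2, Primary Endpoint Analysis) plans the PP analysis as a sensitivity analysis of the primary endpoint in generally compliant participants. With planned arms of 30, 30 and 20, one or two misplaced participants are visible in the result.

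**Working it through.** **The plan's own figure.** The plan gives no number for the PP set. Its only calculated figure is power of at least 90% for a 35-point difference (SAP Section 3: 20 placebo, 30 active, two-sided alpha 0.10). With an unpooled Z-test, power = Φ(0.35/SE − 1.645).
- 5% vs 40%: SE = √(0.05×0.95/20 + 0.40×0.60/30) = 0.1019, power 96.3%.
- 10% vs 45%: SE = √(0.10×0.90/20 + 0.45×0.55/30) = 0.1129, power 92.7%.

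A pooled approximation gives 91.8% and 87.6%; exact enumeration of the pooled test gives 94.8% and 90.2%. The figure reproduces with the unpooled or exact calculation, and this point does not depend on it.

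**Dose arithmetic.** Once-daily dosing for 16 weeks is taken as 16 × 7 = 112 doses (an assumption). The 80% floor is 0.80 × 112 = 89.6, so 90 doses pass (80.4%) and 89 do not (79.5%). The protocol's over-dosing level is 1.20 × 112 = 134.4 doses. Three hypothetical participants:

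| Participant | Compliance | Under Table 1 |
|---|---|---|
| A: stops at Week 8 for lack of efficacy, took 20 of 56 doses due | 20/56 = 35.7% | In, through the second branch; non-responder |
| B: completes, took 88 of 112 | 88/112 = 78.6% | Out |
| C: completes, repeatedly took 120% or more | ≥120% | In, through the first branch |

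SAP 5.3.3.4 removes only ICE 3 participants, so A and C stay.

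**Within-arm size.** The documents give no ICE or compliance counts. Assume a PP arm of 27 that contains one participant like A. With r responders, removing A changes the rate from r/27 to r/26. The planning range for active treatment is 40% to 80% (SAP Section 3).
- r = 11: 11/27 = 40.7%, 11/26 = 42.3%; A costs 1.6 points.
- r = 19: 19/27 = 70.4%, 19/26 = 73.1%; A costs 2.7 points. Two such participants cost 5.6 points (19/25 = 76.0%).

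**Effect on the difference.** Start from 30 active and 20 placebo with a 35.0-point difference, and remove waived non-responders from each arm. Responders are 12 and 1 at 40% vs 5%, and an expected 13.5 and 2 at 45% vs 10%.

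| Removed (active, placebo) | 40% vs 5% | 45% vs 10% |
|---|---|---|
| 1, 4 | 12/29 − 1/16 = 35.1 | 13.5/29 − 2/16 = 34.1 |
| 2, 4 | 12/28 − 1/16 = 36.6 | 13.5/28 − 2/16 = 35.7 |
| 3, 2 | 12/27 − 1/18 = 38.9 | 13.5/27 − 2/18 = 38.9 |
| 4, 1 | 12/26 − 1/19 = 40.9 | 13.5/26 − 2/19 = 41.4 |

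These rows remove every waived participant, so they exceed what a correction limited to the non-adherent ones would do.

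**Over-takers.** At 40% vs 5%, removing one active over-taker gives 11/29 − 1/20 = 32.9 points if that participant responded and 12/29 − 1/20 = 36.4 if not.

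**The case against.** The waiver is deliberate and fits the composite strategy. Deleting it would drop genuine treatment failures after randomization and usually raise the PP response rates. That stands: the waiver should be narrowed, not removed.

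A reader might infer that everyone admitted by the second branch is noncompliant. The documents do not support that. Protocol 6.4 counts missed prescribed doses and exempts doses withheld for safety, and SAP 6.7 does not define the denominator after an early stop. Someone who took every dose until an ICE 1 stop need not be noncompliant. The mismatch is clear only for those already below 80% before the stop, and for over-takers.

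A reader might also infer that the rule biases the PP treatment effect in one direction, by dilution. It does not follow. The estimand is a difference from placebo, the waiver applies in every arm, and stops for lack of efficacy may well be more common on placebo. The table above includes a case where removing the waived participants shrinks the difference.

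Other provisions help in part. Compliance is checked at each treatment visit, and a stop imposed for non-adherence would be ICE 3 and excluded. Receiving an incorrect dose is a major deviation identified before database lock (SAP Appendix 4). The last Table 1 bullet could admit a further criterion. None of these fixes the PP rule in advance: that bullet has neither content nor a deadline, and the deviation list is not tied to PP membership.

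**Conclusion.** The point holds in a limited form. Table 1 admits two kinds of participant who do not belong in a set defined by compliance: those below 80% before an ICE 1 or 2 stop, and those who meet the protocol's over-dosing definition. The first kind always lowers the PP response rate of their own arm, by about 1.6 to 2.7 points each under the assumed arm of 27 with 11 to 19 responders. The sign of the effect on the active-placebo difference is not determined, and over-takers can move it either way. How many such participants there will be is unknown.

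It would be wrong to read this as a threat to the primary result. The FAS analysis, the type I error rate and the power do not use the PP set. This is a correctable inconsistency in a sensitivity analysis, worth settling because the protocol left the detail to the SAP.

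**What to change.** Before unblinding, replace the dosing criterion in SAP Table 1 with wording to this effect:

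*At least 80% of the doses scheduled from first dose to Week 16 or, for participants who discontinued study intervention because of ICE 1 or 2, to the date of that discontinuation. Doses withheld for safety reasons are not counted as missed (protocol 6.4). Participants who meet the protocol 6.4 over-dosing definition (20% or more above the prescribed amount, intentionally or repeatedly, as judged by the investigator) are excluded.*

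This keeps the waiver only for doses not taken after the stop and settles the denominator for early stoppers. Tying the cut-off to discontinuation, not to the ICE itself, keeps participants with ICE 2 who continue dosing under the full 80% test. Citing the protocol's over-dosing definition, instead of a flat 120% limit, preserves the investigator's judgement. The non-responder rule stays for ICE 1 and 2 participants who qualify. Any criterion added under the last bullet should also be fixed before unblinding.

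The cost is a short wording change. Returned-tablet counts and dosing diaries are already collected, and SAP 5.3.2.1 already plans a list of participants with ICEs. Protocol 6.4 does not say where the over-dosing judgement is recorded, so the sponsor should confirm that it is captured. The PP set may lose one or two participants.

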## 4.2. Scientific Rationale for Study Design

### Blinding, Control, Study Phase/Periods, Intervention Groups

A placebo control will be used to establish the frequency and magnitude of changes in clinical endpoints that may occur in the absence of active intervention. Randomization will be used to minimize bias in the assignment of participants to intervention groups, to increase the likelihood that known and unknown participant attributes (eg, demographic and baseline characteristics) are evenly balanced across intervention groups, and to enhance the validity of statistical comparisons across intervention groups. Blinded intervention will be used to reduce potential bias during data collection and evaluation of clinical endpoints.

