#### **5.7.4. Biomarkers**

Planned biomarker analyses may be deferred if emerging study data show no likelihood of providing useful scientific information. Any biomarker samples received by the contract vendor or sponsor after the cutoff date will not be analyzed, and therefore, excluded from the biomarker analysis.

Change in biomarkers over time will be summarized by treatment group. Associations between baseline levels and changes from baseline in select markers and response to treatment will be explored. The analyses will aim to identify biomarker relevant to treatment. Results of biomarker analyses will be reported in separate technical reports.

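### SAP Table 1 defines the PD Analysis Set by receipt of JNJ-77242113, so a literal reading leaves placebo out of the exploratory biomarker summaries

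*SAP*

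**What the plan says.** SAP Section 4 introduces its table of populations with "Unless specified otherwise, data included in the analyses for the study are briefly summarized below", so the sets in that table are the defaults. Two wordings of eligibility appear there:

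- FAS and Safety Analysis Set: "All randomized participants who took at least 1 dose of study intervention". Placebo is a study intervention, so placebo participants qualify.
- PD Analysis Set: "All randomized participants who received at least 1 dose of JNJ-77242113". A participant who took only placebo does not qualify. No evaluable sample is required, although the PK and Immunogenicity sets both require one.

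The biomarker objective in SAP 1.1 is "To explore treatment effects of an oral tablet formulation of JNJ-77242113 on biomarkers in participants with moderate-to-severe plaque psoriasis", and its endpoint is "Change from baseline in levels of skin and blood biomarkers". SAP 5.7.4 plans the analysis: "Change in biomarkers over time will be summarized by treatment group". That section names no analysis set and does not list the groups. Protocol 9.4.6 likewise plans the summary by treatment group. Protocol 9.3 defines no PD set, and SAP Appendix 2 (changes to protocol-planned analyses) reads N/A.

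**The concern.** Leaving placebo out makes sense for a PK set, because a placebo participant has no drug concentration to summarize. It does not carry over to pharmacodynamics, where the placebo group is the reference for what biomarkers do over 16 weeks without drug.

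If the default set is applied as written, the biomarker tables show two active groups and no control. A fall seen at both doses could then not be separated from change that would have happened anyway. The same weakness reaches the planned exploration of how baseline levels and biomarker changes relate to response: without placebo, a marker that merely tracks improvement looks like one that the drug moves. Placebo participants who consent to the skin substudy would also have given biopsies that fall outside the set named for PD.

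**Working it through.** This is a question of definitions, so the check is a count followed by a comparison of sections.

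**Count.** Inputs are the target of 80 participants and the "3:3:2 ratio (30:30:20) using dynamic central randomization" (SAP 1.2).

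- Arm sizes: 80 × 3/8 = 30 (10 mg), 80 × 3/8 = 30 (50 mg), 80 × 2/8 = 20 (placebo). This reproduces the plan's 30:30:20.
- PD set as written: 30 + 30 + 0 = 60.
- PD set if defined on study intervention, as the FAS is: 30 + 30 + 20 = 80.
- Difference: 80 − 60 = 20 participants; 20/80 = 25% of those randomized and 20/20 = 100% of the control group.

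These are upper limits. Serum sampling is scheduled for everyone, but skin and whole-blood sampling are optional substudies whose uptake is not stated.

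**Which set governs SAP 5.7.4?**

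| Section | Names its set? | Lists its groups? |
|---|---|---|
| SAP 5.7.1 Pharmacokinetics | Yes, the PK set | Yes, 10 mg and 50 mg only |
| SAP 5.7.2 Immunogenicity | Yes, the Immunogenicity set | No |
| SAP 5.7.3 PK/PD | No | No |
| SAP 5.7.4 Biomarkers | No | No |

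The PD Analysis Set appears only in Table 1. With nothing else specified in 5.7.4, the default rule points to the set whose name matches the data, and that set has no placebo participants. The reference to treatment group does not settle the matter: SAP 5.7.1.1 also tabulates plasma concentrations per treatment group, and the groups it goes on to list are the two active ones.

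**Are placebo samples available?** The Schedule of Activities plans serum biomarkers at Weeks 0, 2, 4, 8, 12 and 16, optional skin biopsies at Weeks 0, 4 and 16, and optional whole-blood samples at Weeks 0, 2 and 4. None is restricted by arm.

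**What else moves?** Nothing. The plan's only power statement concerns PASI 75, and the efficacy analyses use the FAS.

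**The case against.** A reader might infer that the biomarker endpoint has no placebo control and cannot show a treatment effect. The documents do not support that, for these reasons:

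- No analysis invokes the PD Analysis Set. The exclusion follows from a default rule, not from an instruction in the biomarker section. Both documents plan the summary by treatment group, and the SAP declares no departure from the protocol. Three-arm tables may well be what the authors intend.
- The row may have been written for the concentration-PD work in SAP 5.7.3, where exposure is needed. The SAP does not say.
- Wording on this point is loose elsewhere: Protocol 9.3 defines the PK and immunogenicity sets by the active drug in its text and by study intervention in its table. One row is weak evidence of a decision to discard the control group.
- Even on the literal reading, the randomized contrast of 10 mg with 50 mg (30 against 30) survives, and Week 0 samples are drawn before dosing, so each active participant supplies a drug-free observation.
- The biomarker objective does not ask for comparison with placebo, whereas the efficacy and safety objectives do. The rationale in Protocol 4.2 ("A placebo control will be used to establish the frequency and magnitude of changes in clinical endpoints that may occur in the absence of active") speaks of clinical endpoints and supports the point only by analogy.

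All of this stands, and it limits the point. It does not remove it. Pre-dose samples show where participants started, not what happens over time without drug, and the contrast of two doses says little if both move a marker to the same extent. A written default that conflicts with the likely intention is still a rule that someone may follow.

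It is also tempting to put a number on how far biomarkers would drift without drug. The documents give no basis for one: entry is selected on PASI, BSA and IGA, not on biomarkers, and no correlation between them is reported.

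**Conclusion.** The point holds in a limited form. Taken literally, the PD Analysis Set excludes all placebo participants, up to 20 of 80, and the default rule together with the silence of SAP 5.7.4 makes it the natural set for biomarker data. Applied that way, it gives two-arm summaries in which change from baseline has no placebo reference, against an objective about treatment effects and a sampling plan that covers every arm.

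This rests on two readings: that JNJ-77242113 in that row means the active drug, as the contrast with the FAS row indicates, and that the Table 1 default reaches 5.7.4. It does not establish that the sponsor intends to drop placebo.

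The consequence is small. The endpoint is exploratory and descriptive, no test is planned, the analyses may be deferred, and results go to separate technical reports. No primary or secondary result, power or alpha changes. The case for acting is that the correction is cheap, and that settling it before unblinding avoids deciding with data in view whether placebo counts.

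**What to change.** - **SAP Table 1:** define the PD Analysis Set as every randomized participant dosed at least once with study intervention, whether JNJ-77242113 or placebo, who has a baseline and one or more later biomarker samples.
- **SAP 5.7.4:** name that set, and state that change from baseline is summarized descriptively for placebo, 10 mg and 50 mg.
- **SAP 5.7.3:** if a set restricted to JNJ-77242113 recipients is wanted for the concentration-PD work, keep it as a separate set labelled PK/PD and name it there.

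The cost is a few lines of SAP text. No extra visits or samples are needed, because collection is already scheduled in all arms, and no formal comparison is added. The documents do not say whether placebo samples were already due to be assayed; if they were not, the assay work is an added cost.
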